6.2.6 REAR Measurement and REAG Calculation

SELF-FIT A & B: Personalization begins with an estimate of hearing acuity obtained through the Jabra Enhance Plus. The hearing acuity measurements are used internally by the device and are not shared with the wearer. Once this step has been completed, devices will apply NAL-NL2 gain prescriptions directly using the estimated hearing acuity to generate the initial fit. Probe-tube microphone measures of the REAR (REAG=REAR-input) will be obtained for a 65-dB speech input using the Audioscan Verifit real-ear measurement system. All probe-tube microphone measures will make use of the custom dome/probe-tube assembly supplied by GN Hearing. (Attachment B for details.)

PRO-FIT: Audiometric thresholds will be imported and the devices programmed using custom device programming software (AlgoLabTest) for NAL-NL2 target gains. Probe-tube microphone measures of the REUR and REAR (REAG=REAR-input) will be obtained for a 65-dB speech input using the Audioscan Verifit real-ear measurement system. All probe-tube microphone measures will make use of the custom dome/probe-tube assembly supplied by GN Hearing. (See Attachment B for details.)

6.2.7 QuickSIN

The subject will be seated in a sound-attenuated booth facing a single loudspeaker. All QuickSIN measures, unaided and aided, will be binaural. The QuickSIN test consists of lists of six sentences that will be played from that loudspeaker at a constant level of 65 dB SPL (at location of subject's head using the method of substitution). This speech level was chosen as one approximating a typical conversational level (60-65 dB SPL) and matching the speech input level used for the REAR measures (65 dB SPL). The level of the co-located background four-talker babble increases across the six sentences for signal-to-noise ratios (SNRs) ranging from +25 to 0 dB SNR (in steps of 5 dB). The subject is asked to repeat each sentence. The audiologist scores whether the subject correctly repeated the predetermined key words in each sentence. The resulting score is interpreted as an SNR loss where a value near 0 indicates better hearing and larger values indicate more difficulty listening in noise.

There are 18 lists of the QuickSIN, but McArdle and Wilson (2006) found four of these to be non-equivalent to the others. The remaining 14 lists will be used as follows. Before the first QuickSIN measure at the end of the initial screening (Visit 1), two lists will be presented as practice lists (Lists 4 and 5). For the remaining 12 lists (Lists 1-3, 6, 8-12, 15, 17, 18), two will be assigned to each of the following conditions: unaided (during initial screen; to permit measures of relative benefit), in-lab initial SELF-FIT A, in-lab initial SELF-FIT B, in-lab initial PRO-FIT (the condition order and list pair assigned for each condition will be randomized for each participant), at end of first 10-to-14-day wear period (Visit 2; either final SELF-FIT A or final PRO-FIT), and at end of

final 10-to-14-day wear period (Visit 3; either final PRO-FIT or final SELF-FIT A). Each QuickSIN score will be based on two lists, 60 keywords, and no lists will be repeated for a given subject.

6.2.7.1 QuickSIN Test Procedure

Four conditions: **Unaided, Self-Fit A, Self-Fit B, Pro-Fit**

- i. Listener will sit in a chair in the center of a sound-treated booth facing the speaker from which the test materials will be elicited (0 degrees azimuth, 1 meter distance).
- ii. Training: To familiarize subjects with the speech task, listeners will be presented with two practice lists (Lists 4 and 5) before commencing with the experimental protocol (Visit 1, Unaided only).
- iii. The test will be presented in a sound field at 65 dB SPL.
- iv. There are six sentences in each list of the QuickSIN and 5 keywords that are scored per sentence, resulting in a total of 30 keywords scored per list. Speech levels are automatically presented at SNRs of +25, +20, +15, +10, +5 and 0 dB, one SNR per sentence. The signal-to-noise ratio (SNR) for which 50% of the presented words are intelligible is calculated by subtracting the number of words correct (out of 30) for a given list from 25.5 (Killion *et al.*, 2004).
- v. The microphone setting will be set to "Wide" (omni-directional) during these measurements.

6.2.8 APHAB

The APHAB is a 24-item self-assessment inventory in which the subject reports the amount of trouble they are having with communication or noises in various everyday situations. Benefit from a hearing aid is calculated by comparing the subject's unaided score to their aided score. Although it is possible to collect unaided and aided scores at the same time by asking the subject to reflect back on unaided listening, we will obtain unaided APHAB scores during Visit 1 prior to initiation of the cross-over wear-time trial.

A sample question is as follows: "When I'm at the dinner table with several people, and I am trying to have a conversation with one person, understanding speech is difficult." For each of the 24 items the subject is asked to select one of the following percentages to indicate how frequently this occurs: Always (99%); Almost Always (87%); Generally (75%); Half-the-time (50%); Occasionally (25%); Seldom (12%); or Never (1%). The APHAB will be administered and scored via a tablet PC or iPad.

The APHAB produces scores for 4 subscales: Ease of Communication (EC), Reverberation (RV), Background Noise (BN), and Aversiveness (AV). To increase reliability, only an APHAB-global score based on all 24 items will be used here.

Three conditions: Unaided (Visit 1), Aided (Visit 2), Aided (Visit 3). These three conditions are: 1) prior to the onset of the wear-time field trial, 2) after the first 10-14-day wear period with the first fitting settings (final-fit SELF-FIT A or final-fit PRO-FIT), and 3) after the second 10-14-day wear period with the other fitting settings (final-fit PRO-FIT or final-fit SELF-FIT A).

6.2.9 Telephone Communication and Music Listening

A custom 2-item survey will be completed during Visits 2 and 3 following the APHAB. This survey assesses the enhancement of telephone communication and music listening by the GN prototype devices and makes use of a 7-point response scale ("Strongly Agree" to "Strongly Disagree") for each item. Prior to the beginning of each phase of the cross-over trial, subjects will be encouraged to use their devices in a wide range of listening conditions during the wear-time period, including using the telephone and listening to music.

6.3 Study Duration and Sites

Given the number of study subjects required within this population and the recruitment capabilities of the sites and sponsor, this investigation is expected to last approximately 90-120 days from enrollment of the first subject to completion of the final study subject. This study includes 3 sites: (1) Northwestern University, Evanston, IL; (2) Sertoma Speech and Hearing Center, Palos Hills, IL; and (3) Vanderbilt University, Nashville, TN.

6.4 Monitoring and Treatment of Subjects with Worsening Clinical Condition

Subjects will be monitored for worsening clinical status, including complaints of decreased hearing or increased tinnitus, via self-report at Visits 2 and 3.

6.5 Withdrawal and Discontinuation Criteria

Study subjects may withdraw voluntarily from the research investigation for any reason and at any time during the investigation.

A study subject may also be removed from the investigation for the following medical or administrative reasons:

- Withdrawal of informed consent
- Request to withdraw from the investigation
- Non-compliance (less than 85%) with, or inability to complete, CIP procedures
- Lost to follow-up
- Adverse event (if the subject experiences an AE that, in the judgment of the Site Investigator, presents an unacceptable consequence or risk to the participant).

If a subject is withdrawn from treatment, the Sponsor will be notified and the date and reason(s) for the withdrawal will be documented. If a subject is withdrawn, efforts will be made to perform all follow-up assessments, if possible. Other procedures may be performed at the Investigator's (or designee's) and/or Sponsor's discretion. The Investigator (or designee) may also request that the subject return for an additional Follow-up visit. All withdrawn subjects will be followed until

resolution of all their AEs or until the unresolved AEs are judged by the Investigator (or designee) to have stabilized.

Subjects who are withdrawn for reasons not related to the investigational treatment may be replaced following discussion between the Investigator and the Sponsor. Subjects withdrawn as a result of AEs thought to be related to the investigational treatment will generally not be replaced.

The following actions must be taken if a subject fails to return to the laboratory for a required study visit:

- The site will attempt to contact the subject and reschedule the missed visit within 3 working days and counsel the subject on the importance of maintaining the assigned visit schedule and ascertain if the subject wishes to and/or should continue in the study.
- Before a subject is deemed lost to follow-up, the investigator or designee will make every effort to regain contact with the subject (where possible, 3 telephone calls and, if necessary, a certified letter to the participant's last known mailing address or local equivalent methods). These contact attempts should be documented in the participant's medical record or study file.
- Should the subject continue to be unreachable, he or she will be considered to have withdrawn from the study with a primary reason of lost to follow-up.

A subject will be considered lost to follow-up if he or she fails to return for scheduled visits and is unable to be contacted by the study site staff.

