The user initiates the self-fitting flow via the App. The Earbud presents the user with a series of tones and the user marks the App on the smartphone screen to indicate when/if a tone is heard. Based on the user's responses to these tones, initial gain settings are applied according to the NAL-NL2 fitting algorithm. This self-assessment of hearing loss does *not* provide the user with feedback about accuracy of their responses, nor does it provide the user with a diagnosis or information about their hearing loss. The information obtained during this process is used only internally to fit the device to the NAL-NL2 prescribed gain by frequency in each ear. Based on the initial prescribed gain, the user will subsequently be given the option to choose between two alternative gain settings, i.e., limited adjustments of the spectral tilt based on their preference while listening to a streamed sound file. The spectral tilt option that is selected can also be changed at any time during device use, from the settings menu.

If the Earbuds are powered on for the first time, i.e., no fitting has been done, the Earbuds will start up with basic settings, and with a small amount of linear gain. User controls and streaming are prohibited until after the self-fitting process has been done.

2.1.1.3 *Fine-tune devices*

An important element with the GN Earbuds is the possibility, after the initial fitting is complete, to fine-tune the devices from the smartphone application. Although there are some differences with respect to the fine-tuning features, the vehicle which is used (standard features, volume control, etc.), will be similar to GN legacy hearing instruments currently in commercial distribution in the U.S.

Features that can be set from the home screen of the smartphone application include overall volume and three frequency responses.

2.1.1.4 *Remote firmware update*

The firmware in the Earbuds can be updated, e.g., to strengthen cybersecurity. A message can be pushed from the Cloud to the smartphone App that an update is available. The update can then be applied.

2.1.1.5 *Charge devices*

The Earbuds are charged with a dedicated Charger. Charging will not take place wirelessly but will take place via a physical connection over Pogo contact pins in the Charger.

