After the final in-lab measures have been completed during Visit 1, 9 subjects at each site will wear the devices with the final-fit SELF-FIT A settings and the other 9 at each site will begin the crossover trial with the final-fit PRO-FIT settings. After the initial 10-to-14-day wear-time trial, the subjects will return to the lab for the measurement of REAG, aided APHAB, and aided QuickSIN during Visit 2. Each subject will then embark on a second 10-to-14-day wear-time period using the devices with the other fitting settings (SELF-FIT A settings if PRO-FIT settings were worn first, and vice versa). Subjects will return after the second 10-to-14-day wear-time period for completion of REAG, aided APHAB and aided QuickSIN measures with this second fitting, during Visit 3.

Subjects will follow the instructions for the "Self-fitting flow" (Section 16.0, Attachment A) to complete SELF-FIT A and SELF-FIT B procedures. After the installation of software on the smartphone, the pairing of the devices to the smartphone, and the physical fit of the devices, no further assistance will be provided to the subject by the professional or research staff until the completion of Visit 1. When Visit 1 has been completed, the subject will be provided with the devices, the charger, the USB-C cable, and a copy of the User's Manual (Attachment A). The research audiologist will answer questions raised by the subject as he or she pages through the manual. Prior to leaving for the first phase of the field trial, the subject will demonstrate to the audiologist that he or she can insert and remove the devices, adjust the

volume with the app, and place the devices in the charger. The audiologist will log any errors made in this verification of basic use and will correct the subject on those errors once, if needed, prior to the subject leaving with the devices.

For the wear-time field trial, subjects will be asked to wear the devices in a variety of listening situations during the trial including while listening to music and while using the telephone. Subjects will be asked to wear their devices a minimum of two hours per day.

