8.3 Missing Data Management

All planned data will be collected as complete and as timely as possible. No imputation of missing data is anticipated.

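### Subjects who cannot complete the unaided self-fit may be removed, and no analysis rule counts them, so their failures can fall out of the REAG and APHAB comparisons in SELF-FIT's favour

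*Combined protocol and SAP*

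**What the plan says.** **Removal.** Section 6.5 introduces its list of grounds with "A study subject may also be removed from the investigation for the following medical or administrative reasons". One ground is "Non-compliance (less than 85%) with, or inability to complete, CIP procedures". The text does not say what the 85% is a percentage of. Section 6.2.5 asks for at least two hours of wear per day but does not link that request to the 85%.

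**Who does the fitting.** The subject carries out SELF-FIT A and B (6.2.3, 6.2.4). Once the app is installed, the devices paired and the physical fit made, "no further assistance will be provided to the subject by the professional or research staff until the completion of Visit 1" (6.2.5). The audiologist carries out PRO-FIT (6.2.2).

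**Replacement and follow-up.** Section 6.5 also states: "Subjects who are withdrawn for reasons not related to the investigational treatment may be replaced following discussion between the Investigator and the Sponsor". The only withdrawals it marks as normally not replaced are these: "Subjects withdrawn as a result of AEs thought to be related to the investigational treatment will generally not be replaced". On data collection it says: "If a subject is withdrawn, efforts will be made to perform all follow-up assessments, if possible".

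**Analysis.** Section 8.1 lists paired equivalence t-tests and crossover non-inferiority t-tests without naming an analysis set. Section 8.3 adds: "No imputation of missing data is anticipated". The endpoints in 3.2 are REAG, APHAB, QuickSIN and adverse events; none counts incomplete self-fits. The separate usability study mentioned in 6.2.1 covers installation, pairing and earbud size, not the self-fitting flow.

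**The concern.** The device is intended for sale and use without professional help (2.3.1), so whether people can complete the self-fit is central evidence. A subject who cannot complete it meets a stated ground for removal. Because the audiologist does the PRO-FIT, inability to complete a fitting falls on SELF-FIT. This makes it an exclusion that depends on how the tested method performed.

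No analysis rule offsets it. With no defined analysis set, no imputation and no count of failures, the paired comparisons can end up resting on those who succeeded. That pulls REAG toward equivalence and APHAB toward non-inferiority. Section 8.4 requires every primary endpoint to be met, so an effect on any one of them could change the overall result.

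Replacement adds a second opening. The text does not say whether a failed self-fit, or low use of the device, is related to the investigational treatment, and the sponsor takes part in that discussion. Section 13.1 also lets Visit 1 results reach the sponsor before the study ends.

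**Working it through.** **1. The plan's own figure.** Section 5.1 gives an APHAB margin of 0.084, root MSE 0.115, expected difference 0, a 2.5% significance level and 80% power with 32 subjects.
- SD of differences: √2 × 0.115 = 0.163, as stated.
- Power from the noncentral t distribution with N − 2 degrees of freedom and noncentrality 0.084 / (0.163/√N): 80.5% at N = 32 and 85.2% at N = 36.

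The sample size reproduces and is not in question. The attrition allowance is 36 − 32 = 4 subjects.

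**2. Shift in REAG.** The limit is 2.5 dB on the mean absolute difference (3.1.1, 3.1.5). The documents give neither a failure rate nor a failure effect, so I assume that k of 36 subjects fail, that each failure would show a difference of d dB if measured unfitted or assigned a value, and that the others average 1.5 dB.

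Mean with failures counted = ((36 − k) × 1.5 + k × d)/36. Mean without them = 1.5. Understatement = k × (d − 1.5)/36, whether the failures are dropped or replaced.

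| k | d (dB) | Understatement (dB) | Share of 2.5 dB |
|---|---|---|---|
| 1 | 5 | 3.5/36 = 0.10 | 4% |
| 2 | 10 | 17/36 = 0.47 | 19% |
| 4 | 10 | 34/36 = 0.94 | 38% |

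In the last row the mean with failures counted is 1.5 + 0.94 = 2.44 dB, still just under the limit. If the others average 2.0 dB instead, three failures at 10 dB give (33 × 2.0 + 3 × 10)/36 = 2.67 dB, and five at 6 dB give (31 × 2.0 + 5 × 6)/36 = 2.56 dB. Both exceed the limit, whereas the mean without the failures stays at 2.0 dB.

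**3. Effect on the APHAB test.** This is a simulation of 40,000 trials of 36 paired differences with SD 0.163. The true difference is 0 in those who can self-fit, failures are assumed to be 0.20 or 0.40 worse with SELF-FIT, and period effects are ignored. The last three columns give the chance of declaring non-inferiority.

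| Failures | Deficit each | Mean over all 36 | Kept | Dropped | Replaced |
|---|---|---|---|---|---|
| 2 | 0.20 | 0.011 | 71% | 83% | 85% |
| 2 | 0.40 | 0.022 | 48% | 83% | 85% |
| 4 | 0.20 | 0.022 | 54% | 80% | 85% |
| 4 | 0.40 | 0.044 | 14% | 80% | 85% |

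In all four rows the mean over all 36 subjects is below 0.084. The table therefore shows how far the chance of passing depends on an unstated analysis rule. It does not show a false claim of non-inferiority.

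**4. Which route reaches which endpoint.** Primary REAG is taken at Visit 1 on initial-fit settings (6.2.3, 6.2.5), before any wear. Inability to self-fit therefore reaches both REAG comparisons, and it reaches APHAB because there are no SELF-FIT A settings to wear. Low wear reaches mainly the field-trial endpoints. It touches REAG only if a removed subject's Visit 1 data are also discarded.

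**The case against.** The strongest reply is that 6.5 is softer than it looks. Removal is optional, follow-up after withdrawal is attempted, and nothing says that a withdrawn subject's data are discarded. Replacement is barred when the reason relates to the investigational treatment, and inability to perform the tested method could well be judged related. Withdrawal dates and reasons are documented (6.5), and complete data per visit are tallied weekly (13.1). All of this stands. It makes the loss possible, not automatic, but it does not say who is analysed or how an incomplete self-fit counts.

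A reader might infer that self-fit failures will be removed and replaced as a matter of course. The replacement condition and the permissive wording do not support that; the gap is that the classification is left open.

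A reader might also infer that low wear biases REAG, or works mainly against SELF-FIT. The REAG timing rules out the first unless Visit 1 data are discarded. As to the second, each subject wears the same device under both fits, so low wear can occur in either period.

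Nor were the primary endpoints built to detect failed self-fits: they compare REAG and APHAB scores. A subject who never finishes the flow has no SELF-FIT value even if never removed, so deleting the removal ground would not solve the problem.

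Finally, every failure count and effect size above is assumed, and some are large: a 0.40 deficit is 0.40/0.163 = 2.5 planned SDs of the difference. That limits what can be said about size, not about direction.

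**Conclusion.** The concern holds in a limited form. The plan permits an outcome-dependent exclusion that, for inability to self-fit, falls on SELF-FIT, and it has no analysis set, missing-data rule or failure count to offset it. The direction favours SELF-FIT. The size cannot be known from the documents: under the assumed 1 to 4 failures of 36 at 5 to 10 dB, with the others at 1.5 dB, mean absolute REAG difference is understated by 0.10 to 0.94 dB against 2.5 dB. Whether this would reverse a result depends on the failure rate and on how close the remaining subjects are to the limit. The plan should be changed before analysis because the remedy is cheap and completion of the self-fit matters for the intended use.

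**What to change.** Leave the withdrawal rule as it is and change the analysis and reporting text in 6.5 and 8.3:

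1. Every subject assigned a sequence stays in the primary analysis with all data obtained, before and after withdrawal. Replacements are additional subjects, not substitutes.
2. Inability to complete the self-fit is classed as related to the investigational treatment for the replacement rule, and the 85% is given a defined measure.
3. The number of incomplete self-fits is reported out of all subjects who started one.
4. A prespecified sensitivity analysis counts incomplete self-fits against SELF-FIT. It is needed because a paired test omits anyone lacking one of the two values, even when all available data are kept.
   - REAG: use the unfitted start-up state, in which "the Earbuds will start up with basic settings, and with a small amount of linear gain" (2.1.1.2), or an unfavourable assigned value. Never use settings retained from an earlier fit. One in-lab order in 5.1 puts PRO-FIT before both self-fits, and SELF-FIT B always follows another fit. If settings persist, which the documents do not address, a failure could be scored as agreement.
   - APHAB: use an unfavourable assigned SELF-FIT difference.
5. The compliant-only analysis is given as a further sensitivity analysis.

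The cost is protocol and SAP wording, one count and two sensitivity analyses. The downside is slightly more variable primary data. The assigned values must be fixed before data are seen.
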